7.1.1. Temporary Interruption of Study Intervention

See Section [6.6](#) for guidelines for withholding study intervention.

7.2. Participant Discontinuation/Withdrawal from the Study

Discontinuation is expected to be uncommon.

A participant may withdraw from the study

- at any time at the participant's own request for any reason or without providing any reason
- at the request of the participant's designee, for example, participant's legally authorized representative
- at the discretion of the investigator for safety, behavioral, compliance, or administrative reasons
- if enrolled in any other clinical study involving an investigational product, or enrolled in any other type of medical research judged not to be scientifically or medically compatible with this study, or
- if the participant dies.

If the participant has not already discontinued the study intervention, the participant will be permanently discontinued from the study intervention at the time of the decision to discontinue the study.

At the time of discontinuing from the study, if possible, the participant will complete procedures for a short-term follow-up visit, as shown in the SoA.

If the participant withdraws consent for disclosure of future information, the sponsor may retain and continue to use any data collected before such a withdrawal of consent. If a participant withdraws from the study, the participant may request destruction of any samples taken and not tested, and the investigator must document this in the site study records.

If a participant is considering withdrawing consent from the study and all further follow-up, the investigator should provide the participant with options for alternative follow-up methods, for example, discontinuation of follow-up clinical visits, but continued follow-up for survival. If the participant does not wish to be contacted for the necessary follow-up questions pertaining to survival, this should be clearly documented.

7.3. Lost to Follow-Up

A participant will be considered lost to follow-up if they repeatedly fail to return for scheduled visits and are unable to be contacted by the study site.

Site personnel or designee is expected to make diligent attempts to contact participants who fail to return for a scheduled visit or were otherwise unable to be followed up by the site.

Site personnel, or an independent third party, will attempt to collect the vital status of the participant within legal and ethical boundaries for all participants randomized, including those who did not get investigational product.

Public sources may be searched for vital status information. If vital status is determined to be deceased, this will be documented, and the participant will not be considered lost to follow-up.

8. Study Assessments and Procedures

Study procedures and their timing are summarized in the SoA Section 1.3.

Immediate safety concerns should be discussed with the sponsor immediately upon occurrence or awareness to determine if the participant should continue or discontinue study intervention.

Adherence to the study design requirements, including those specified in the SoA, is essential and required for study conduct.

All screening evaluations must be completed and reviewed to confirm that potential participants meet all eligibility criteria. The investigator will maintain a screening log to record details of all participants screened and to confirm eligibility or record reasons for screening failure, as applicable.

8.1. Efficacy Assessments

8.1.1. Response Assessment

All participants must have clinical examination and response assessments during the course of treatment, while on study, and during follow-up as indicated in the SoA.

The investigator will conduct radiologic assessments locally and send images for central assessment according to the Imaging Manual.

The investigator will assess response using the iwCLL 2018 response criteria (Hallek et al. 2018), based on

- disease and symptom-focused physical examination
- imaging
- hematology results, and
- bone marrow examinations, as applicable.

See Section 8.1.4 for iwCLL response criteria guidance. Response assessments will include CR, CRi, nPR, PR, PR-L, SD, or PD (Cheson et al. 2012; Hallek et al. 2018).

Disease progression

Constitutional symptoms alone do not define PD. With approved BTK inhibitors, lymphocytosis and leukocytosis are well-documented on-target effects that occur early during treatment administration. These reactions are not reflective of PD in the absence of other signs of PD, for example, splenomegaly, enlarging lymph nodes, isolated new lymphocytosis, or disease-related constitutional symptoms and will not be considered PD.

Sponsor verification of progressive disease may be requested.

Richter's transformation

If Richter's transformation is suspected, the investigator should confirm the diagnosis using local standard of care procedures and document this in the EDC. If a PET-CT scan is performed, the results of this scan should be captured in the EDC.

8.1.2. Radiologic Imaging

To evaluate treatment response and recurrence, radiologic imaging is required until

- disease recurrence or progression
- the start of a new anticancer therapy
- death, or
- study completion.

Radiologic imaging may also be obtained as clinically indicated, which may be before the next scheduled scan.

Radiologic imaging timing should follow calendar days from randomization and should not be recalculated based on date of previous scans.

Preferred method of imaging

CT scan with IV contrast agent is the preferred method of assessment with scans of neck, chest, abdomen, and pelvis. However, MRI with contrast is acceptable if CT scan with contrast agent is contraindicated.

Use the same method of imaging throughout the study for each individual participant.

8.1.3. Bone Marrow Biopsy

Complete response assessment by the investigator should rely on local evaluation of the bone marrow.

8.1.4. iwCLL Response Criteria Guidance

Parameter	Group A				Group B		
	Lymph nodes	Liver or spleen size ^a	Constitutional symptoms	Circulating lymphocyte count	Platelet count	Hemoglobin	Marrow
CR When all criteria are met.	None ≥1.5 cm	Spleen size <13 cm. Liver size normal	None	Normal ^b	≥100 × 10 ⁹ /L	≥11.0 g/dL not transfused and without erythropoietin	Normo-cellular, no CLL cells, no B- lymphoid nodules
PR^c When at least 2 of the criteria in Group A and 1 criterion in Group B improve after receiving study intervention.	Decrease ≥50% from baseline ^d	Decrease ≥50% from baseline	Any	Decrease ≥50% from baseline	≥100 × 10 ⁹ /L or increase ≥ 50% over baseline	≥11.0 g/dL or increase ≥50% over baseline	Presence of CLL cells, or B- lymphoid nodules, or test not done

Parameter	Group A				Group B		
	Lymph nodes	Liver or spleen size ^a	Constitutional symptoms	Circulating lymphocyte count	Platelet count	Hemoglobin	Marrow
PD^e When at least 1 criterion is met.	Increase $\geq 50\%$ from nadir ^f	Increase $\geq 50\%$ from nadir	Any	Increase $\geq 50\%$ over nadir	Decrease of $\geq 50\%$ from baseline secondary to CLL	Decrease of ≥ 2 g/dL from baseline secondary to CLL	Increase of CLL cells by $\geq 50\%$ on successive biopsies
SD When all criteria are met.	Change from -49% to +49%	Change from -49% to +49%	Any	Change from -49% to +49%	Change from -49% to +49%	Increase < 11.0 g/dL or $< 50\%$ over baseline, or decrease < 2 g/dL	No change in marrow infiltrate

Abbreviations: CR = complete remission; CLL = chronic lymphocytic leukemia; PD = progressive disease; PR = partial remission; SD = stable disease.

- a Spleen size is considered normal if < 13 cm. There is no established international consensus of the size of a normal liver. Evaluate the liver size by imaging and manual palpation.
- b Normal lymphocyte count should be $< 4 \times 10^9/L$. CR also requires absolute neutrophil count to be $\geq 1.5 \times 10^9/L$.
- c At least 2 of the parameters of Group A and 1 parameter of group B need to improve if previously abnormal. If only 1 criterion from both Groups A and B is abnormal before receiving study intervention, then at least 1 of those criteria improves after receiving study intervention.
- d Sum of the products of 6 or fewer lymph nodes, as evaluated by imaging and physical examination in clinical studies or by physical examination in general practice.
- e Appearance of any new lesion, such as enlarged lymph nodes (≥ 1.5 cm), splenomegaly, hepatomegaly, or other organ infiltrates. Transient increases of lymph node size during treatment with novel inhibitors may occur and should not be counted as PD. Isolated new lymphocytosis occurring early in the treatment course will not be used as criteria for determining PD. Constitutional symptoms alone do not define PD.
- f Any lymph node greater than 1.5 cm of any previous site that increases by $\geq 50\%$ from nadir in greatest determined diameter.

Source: Hallek et al. 2018.

Additional response criteria

CRi

CRi is when a participant fulfills all criteria for a CR, with persistent anemia, neutropenia, or thrombocytopenia, and the investigator relates the cytopenia to study intervention and not due to the underlying disease.

nPR

nPR is when a participant fulfills all criteria for a CR, but the bone marrow biopsy or aspirate shows B-lymphoid nodules with residual disease.

PR-L

BTK inhibitors are known to cause lymphocytosis, defined as an increase in the number of blood lymphocytes by 50% or more with at least $5 \times 10^9/L$ B lymphocytes, due to redistribution of lymphocytes.

In BTK inhibitors or compounds with similar mechanism of action, initial absolute lymphocyte count progression with associated PR in other categories during therapy is usually indicative of PR-L (Cheson et al. 2012).

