 5. Must have laboratory test results within the ranges described in this table. Results from the most recent laboratory tests prior to enrollment will be used for eligibility.

Test	Result
Hematology	
Absolute neutrophil count	$\geq 0.75 \times 10^9/\text{L}$, or $\geq 0.50 \times 10^9/\text{L}$ in patients with documented bone marrow involvement considered to impair hematopoiesis. Granulocyte-colony stimulating factor (G-CSF) support is permitted in patients with documented bone marrow involvement.
Platelet count	$\geq 50 \times 10^9/\text{L}$, or $\geq 30 \times 10^9/\text{L}$ in patients with documented bone marrow involvement considered to impair hematopoiesis. Transfusion support is permitted in patients with bone marrow involvement.†
Hemoglobin level	$\geq 8 \text{ g/dL}$ ($\geq 80 \text{ g/L}$), or $\geq 6 \text{ g/dL}$ in patients with documented bone marrow involvement considered to impair hematopoiesis. Transfusion support is permitted in patients with bone marrow involvement.†
† Patients must be responsive to transfusion support if given for thrombocytopenia or anemia. Patients known to be refractory to transfusion support are not eligible. If the patient is cypogenic, there should be no evidence of myelodysplasia or hypoplastic bone marrow.	
Hepatic	
Total bilirubin	$\leq 1.5 \times \text{ULN}$, or $\leq 3 \times \text{ULN}$ with documented liver involvement and/or evidence of Gilbert’s disease.
ALT and AST	$\leq 3.0 \times \text{the ULN}$, or $\leq 5 \times \text{ULN}$ with documented liver involvement.
Renal	
Creatinine clearance	$\geq 30 \text{ mL/min}$ Using Cockcroft/Gault formula: $(140 - \text{age}) \times \text{body weight (kg)} \times 0.85$ (if female) serum creatinine (mg/dL) $\times 72$

Abbreviations: ALT = alanine aminotransferase; AST = aspartate aminotransferase; ULN = upper limit of normal.

6. **CCI** [REDACTED]

Previous treatment

7. Prior CLL/SLL treatment
 - have received at least 1, but not more than 3 lines of, treatment for CLL/SLL, and
 - have received a covalent BTK inhibitor.

8. Have had a washout period planned before randomization for these treatments
 - previous BTK inhibitor - 5 half-lives or 1 week, whichever is longer
 - targeted agents or cytotoxic chemotherapy - 5 half-lives or 2 weeks, whichever is longer
 - therapeutic antineoplastic monoclonal antibodies - 5 half-lives or 4 weeks, whichever is longer, and
 - palliative limited field radiation – 1 week.

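### The PR row, unlike the CR hemoglobin cell, does not exclude counts supported by transfusion or erythropoietin, so such a count could complete a PR in the primary ORR

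*Supplement*

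**What the plan says.** The response table in protocol Section 8.1.4 treats supported blood counts differently by row and by cell:

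- CR, hemoglobin: "≥11.0 g/dL not transfused and without erythropoietin".
- PR, hemoglobin: "≥11.0 g/dL or increase ≥50% over baseline", with nothing on transfusion or erythropoietin.
- PR, platelets: a fixed threshold of 100 × 10^9/L "or increase ≥ 50% over baseline", with nothing on transfusion.
- CR, platelets: the same fixed threshold, with nothing on transfusion.

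The PR rule applies "When at least 2 of the criteria in Group A and 1 criterion in Group B improve after receiving study intervention". Footnote c adds "At least 2 of the parameters of Group A and 1 parameter of group B need to improve if previously abnormal" and relaxes the count when only one criterion was abnormal at the start.

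Section 5.1, criterion 5, says of both platelets and hemoglobin: "Transfusion support is permitted in patients with bone marrow involvement". It adds "Patients must be responsive to transfusion support if given for thrombocytopenia or anemia". With marrow involvement the entry floors are 6 g/dL and 30 × 10^9/L.

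Section 9.3.3 counts PR in the investigator-assessed ORR, the primary endpoint.

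**The concern.** The CR hemoglobin cell shows that the sponsor saw the problem of supported counts and dealt with it in one place. A site that reads the two rows side by side may conclude that a supported value is acceptable for PR.

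The people for whom this matters are recruited on purpose. Progressive marrow failure is one of the treatment indications in Section 5.1, criterion 3. Those who are transfused at entry must be people whose counts respond to transfusion. In a participant with two genuine Group A improvements and a persistent cytopenia, a post-transfusion count could supply the missing Group B element. That participant would then count as a responder although the marrow had not recovered.

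The trial is open-label and its primary endpoint is the investigator's assessment. Section 8.1.1 sends images for central assessment but describes no central check of blood counts against transfusion.

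**Working it through.** **Is the condition stated anywhere else?** I looked for text that would exclude supported counts for PR:

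- Section 8.1.4, footnotes a to f and the additional response criteria: none.
- Section 3, primary estimand and its intercurrent events: transfusion and growth factor are not mentioned.
- Sections 6.9.1 and 6.9.2: transfusion and erythropoietin are not listed as prohibited.
- Section 6.9: name, reason, route and dates of each therapy are collected, but nothing links them to response.
- Section 9.3.3: none.
- Section 9.3.4 defines a baseline value for safety. No text says whether a post-transfusion count may serve as the baseline for response.

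**Can a supported count meet the PR cell?** The inputs are the entry floors with marrow involvement (Section 5.1) and the 50% rule (Section 8.1.4).

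- Hemoglobin: 6.0 × 1.5 = 9.0 g/dL, which meets the cell while still below 11.0 g/dL.
- Platelets: 30 × 1.5 = 45 × 10^9/L, which meets the cell while still below 100 × 10^9/L.

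These examples take an unsupported baseline. If the baseline was itself raised by transfusion, a 50% rise is harder to reach, so the missing rule can also cost a genuine PR.

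**What does one case weigh?** The plan's power figure cannot be reproduced, because the ratio, numbers per arm, response rates, alpha and power are redacted. Assuming equal allocation:

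- 249 / 3 = 83 per arm.
- 1 / 83 = 1.2 percentage points of ORR per case.

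**Equal misclassification (illustration only).** Let a share m of true non-responders in every arm be credited with a PR. Observed ORR = p + m(1 − p), so the observed difference = (1 − m)(p1 − p2). Assume p1 = 75% and p2 = 55%, 83 per arm and two-sided alpha 0.05. Power is Φ[(d − 1.96·SE0)/SE1], with pooled SE0 and unpooled SE1.

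| m (assumed) | ORR, higher v lower | Difference | Power |
|---|---|---|---|
| 0 | 75.0% v 55.0% | 20 points | 77.6% |
| 5% | 76.25% v 57.25% | 19 points | 74.3% |
| 10% | 77.5% v 59.5% | 18 points | 70.8% |
| 20% | 80.0% v 64.0% | 16 points | 63.3% |

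No value of m can be taken from the documents.

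**Unequal misclassification.** Each case in a lower-dose arm only narrows the difference by 1.2 points. Each case in the 200 mg arm only widens it by 1.2 points.

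**The case against.** The strongest reply is that Section 8.1.1 makes iwCLL 2018 the standard and Section 8.1.4 calls its table guidance taken from that source. The published criteria may deal with supported counts, and editing the cells might depart from them. That source is not available here, so this cannot be settled. It remains true that the table is what sites are given and that it differs between its own rows. The sponsor should check any added wording against the source.

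The mechanism is also narrow, and this stands. A PR due only to transfusion needs two Group A improvements (fewer only under footnote c), no genuine Group B improvement, and a supported count at the assessment. It also needs the absence of a PR on unsupported counts at any other assessment in the best-response window. Entry on transfusion support is limited to marrow involvement.

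Section 9.3.1 leaves the handling of spurious data to the SAP, which is not shown. A sensitivity analysis could be placed there, but the response definition itself sits in the protocol.

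The PR marrow cell accepts a test not done, which might seem to satisfy Group B without any blood count. The rule requires a criterion to improve, and an untested marrow cannot show that.

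Two stronger readings are tempting and are not supported:

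- *False progression.* A reader might infer that a transfused baseline followed by a return to the usual level would be scored as progression. The cell reads "Decrease of ≥ 2 g/dL from baseline secondary to CLL", so the fall must be attributed to the disease. Section 1.3.1 also provides marrow biopsy to confirm progression due to cytopenia.
- *A known direction of bias.* A reader might infer that lower doses leave more people transfused, so that the 200 mg advantage is hidden. Section 8.3.3 also names cytopenia as a class effect of the drug, so more transfusion at 200 mg is equally possible.

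**Conclusion.** The point holds as a gap in the definition of the primary endpoint. As written, Section 8.1.4 lets a hemoglobin or platelet count raised by transfusion or growth factor supply the Group B element of a PR, although the CR hemoglobin cell excludes such values.

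The size is unknown and probably small, because Group A improvement is still required. The figure of about 1.2 points per case rests on the assumption of 83 per arm. The dilution table rests on assumed response rates and assumed shares, and shows only how the effect scales. Nothing in the documents gives a count of affected participants or a direction of bias between doses. The correction is still worth making, because the rule can misclassify a response in an open-label, investigator-assessed primary endpoint and is cheap to mend.

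**What to change.** 1. In Section 8.1.4, give the PR hemoglobin cell the same condition on transfusion and erythropoietin as the CR hemoglobin cell. Add a no-transfusion condition to the CR and PR platelet cells. One equivalent line in footnote c would do instead.
2. State that baseline and response counts used for Group B must be free of recent transfusion or growth-factor support. Pre-specify one look-back window, identical for all arms. The documents give no basis for its length, so the sponsor must choose and justify it.
3. Check the counts behind each PR against the therapy dates collected under Section 6.9, and confirm that this collection captures transfusions. State whether the investigator's assessment or the check prevails when they disagree.

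This changes how counts are scored and does not restrict anyone's supportive care. The cost is a few words in the table and a derivation check on data largely collected already. The downside is that a few transfused participants will not be credited with a PR, so ORR may be slightly lower.

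### The lymphocyte criterion for PD in Section 8.1.4 has no minimum count, so a rise within the normal range can meet PD while also satisfying the CR lymphocyte cell

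*Supplement*

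**What the plan says.** The response table in Protocol Section 8.1.4 declares PD "When at least 1 criterion is met". For the circulating lymphocyte count, the criterion is "Increase $\geq 50\%$ over nadir" and nothing more. The SD row asks for a lymphocyte change between -49% and +49%.

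Other parts of the same section do carry limits:

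- Footnote b, on the CR lymphocyte cell: "Normal lymphocyte count should be" below 4 x 10^9/L.
- Footnote f, on the nodal PD cell: "Any lymph node greater than 1.5 cm of any previous site that increases by" at least 50% from nadir.
- The platelet and hemoglobin PD cells require the fall to be secondary to CLL.
- The PR-L text describes lymphocytosis as "defined as an increase in the number of blood lymphocytes by 50% or more with at least" 5 x 10^9/L B lymphocytes. The text does not link this definition to PD.

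Two passages restrict the PD row. Footnote e says: "Isolated new lymphocytosis occurring early in the treatment course will not be used as criteria for determining PD". Section 8.1.1 describes lymphocytosis and leukocytosis as effects seen early on BTK inhibitors and adds: "These reactions are not reflective of PD in the absence of other signs of PD".

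Section 8.1.1 has the investigator assess response by iwCLL 2018 and points to Section 8.1.4 for guidance. Sponsor verification of PD is optional.

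**The concern.** A ratio to nadir with no lower limit becomes easy to trigger in absolute terms once the count is low. A participant whose count has normalized and then moves from 1.2 to 1.9 x 10^9/L has risen by 58% and meets PD as written. The same count is normal under footnote b and satisfies the CR lymphocyte cell. No text says which row prevails.

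PD has several consequences in this plan. It is an event for DOR (Section 9.3.4) and for PFS (Section 9.3.6.1). It closes the window for best overall response (Section 3) and ends required imaging (Section 8.1.2). It is also a listed reason for permanent discontinuation of study intervention (Section 7.1). The trial is open-label and the endpoints are investigator-assessed, so sites that read the cell differently would date progression differently.

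**Working it through.** The documents give no figure for this criterion, so there is nothing to reproduce. Two checks apply: one uses only the documents' thresholds, and the other is illustrative.

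**1. Threshold arithmetic (document figures only)**

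- PD threshold = 1.5 x nadir (PD row).
- Normal count: below 4 x 10^9/L (footnote b).
- The rows overlap when 1.5 x nadir < 4, that is, when nadir < 4/1.5 = 2.67 x 10^9/L.
- Examples: nadir 1.0 gives PD at 1.5; nadir 2.0 gives PD at 3.0. Both are normal counts. Nadir 3.0 gives PD at 4.5, which is outside the normal range.

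**2. Do the exemptions cover the overlap?**

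- Footnote e is limited to isolated new lymphocytosis early in treatment. A rise after the count has normalized need not be early.
- By the section's own definition, lymphocytosis needs at least 5 x 10^9/L B lymphocytes. A total count below 4 x 10^9/L cannot reach that, so a normal-range rise is not lymphocytosis and the exemption does not name it.
- Section 8.1.1 also concerns early drug-induced lymphocytosis. Its examples of other signs of PD include isolated new lymphocytosis itself, which leaves the exemption unclear.

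**3. How often a stable participant would meet the literal criterion (illustrative)**

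Assumptions, none of them from the documents: no change in disease; independent lognormal counts with median 1.5 x 10^9/L; within-person CV of 10% to 30%; 400,000 simulated participants per setting. A participant is flagged if any count is at least 1.5 times the lowest earlier count. The log-scale SD is sigma = sqrt(ln(1 + CV^2)).

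The numbers of counts match the schedule of activities: 3 for C5, C9 and C13 (imaging visits); 4 when C6 is added; 6 when C17 and C21 are added as well.

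Hand check for one pair of counts: P = 1 - Phi(ln 1.5 / (sigma x sqrt 2)). At CV 20%, sigma = 0.198, so P = 1 - Phi(0.405/0.280) = 7.4%. Repeated looks raise it as follows:

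| CV | 3 counts | 4 counts | 6 counts |
|---|---|---|---|
| 10% | 0.6% | 1.1% | 2.6% |
| 15% | 7% | 12.5% | 25% |
| 20% | 18% | 29% | 51% |
| 25% | 28% | 43% | 68% |
| 30% | 36% | 54% | 78% |

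Nearly all flags fall below 4 x 10^9/L. If a floor of 5 x 10^9/L is applied to the total count as a stand-in, the share is 0.01% or less in every cell.

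**4. Does the model favor or penalize a dose?**

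The rule is a ratio, so with a constant CV the flag rate does not depend on the level of the count. With the median set to 20 x 10^9/L instead of 1.5, the 4-count rates at CVs of 15%, 20%, 25% and 30% are 12.6%, 29.4%, 43.5% and 53.9%, the same within simulation error. At that level a floor of 5 x 10^9/L removes none of the flags.

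**The case against.** **The table is guidance.** Response is an investigator judgment under iwCLL 2018 that combines examination, imaging, hematology and, where applicable, marrow. Sponsor verification is available, and nothing says a program scores the cell. This stands, and it means the simulated rates show exposure under literal use; they do not forecast events. It does not remove the conflict, because Section 8.1.4 is where Section 8.1.1 sends the investigator. How the full cited criteria treat normal-range counts cannot be checked from these documents.

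**Other cells are terse too.** The liver/spleen PD cell also has no absolute floor, so the lymphocyte cell is not unique. This stands. The lymphocyte cell still conflicts with an explicit normal limit in the same table.

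**The size is uncertain.** The CV is assumed, and at 10% the share is only 0.6-2.6%. This stands.

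**A reader might infer that every 50% rise counts as PD.** It does not: early isolated lymphocytosis is exempt.

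**A reader might infer that the best responders, and hence the dose that clears lymphocytes most, collect the most false events.** The documents do not show this, and the constant-CV model gives the same rates at any count level.

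**A reader might infer damage to the primary comparison.** PD does close the BOR window, but a rise from a normalized nadir would usually follow a recorded response, so ORR would seldom change.

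**Conclusion.** The point holds as a defect in the wording of the PD criterion. As written, and outside the early-lymphocytosis exemptions, a participant with a nadir below 2.67 x 10^9/L can meet PD with a count that the same table calls normal. That conclusion rests only on the documents' own thresholds.

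If sites apply the cell literally, the result is false DOR and PFS events and possible unnecessary treatment stops. For stable participants the illustrative share is 0.6-36% with 3 counts, 1-54% with 4 and 3-78% with 6. These ranges depend on assumed CVs of 10% to 30%, independent counts and literal scoring. Confidence is high in the contradiction and low in its size. The endpoints mainly exposed are secondary (DOR) and exploratory (PFS). An effect on ORR is possible but less likely, and no difference between doses is demonstrated. The point should be corrected, but it does not undermine the primary analysis.

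**What to change.** Reconcile five places: the PD lymphocyte cell, footnote b, footnote e, the PD text in Section 8.1.1 and the lymphocytosis definition in the PR-L text. The outcome should be that a rise within the normal range cannot count as PD, and the text should state whether the 5 x 10^9/L condition applies to PD.

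Express the condition in terms of the count collected. The definition refers to B lymphocytes, but the hematology panel in Appendix 2 lists lymphocytes with no B-cell subset. Because PD is also a reason to stop study intervention (Section 7.1), the clinical team should settle the exact condition; no threshold is prescribed here. Use the same rule when deriving BOR, DOR and PFS.

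The cost is one clause in the table, matching wording in Section 8.1.1 and the site guidance, and one derivation rule. No new data are needed if the rule uses the total lymphocyte count. The downside is small: a relapse visible only in blood may be dated slightly later.
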